10.0 Data Monitoring Plan

This is a single arm phase II study in patients with MDS who have failed therapy with or are intolerant of hypomethylating agents.

Primary objective: complete response (CR); overall survival.

Secondary objective: duration of response; relapse-free survival; safety.

It will be postulated that the treatment can achieve a CR rate of 20% and a median overall survival time of 6 months.

A maximum of 80 patient will be accrued at a rate of 2 to 5 patients per month (maximum accrual period 3.33 yrs). The CR, overall survival and toxicity will be monitored during the study, and all data will be used to update the prior distributions for toxicity and efficacy parameters. The study will be stopped for toxicity and futility based on the following stopping rules.

Efficacy monitoring

Complete response and overall survival will be monitored separately. The method of Thall, Simon, and Estey [9] will be used to monitor response and Bayesian time-to-event model [10] will be used to monitor overall survival.

a. CR

CR will be monitored in all pts using the method of Thall et al.[9] Denote the probability of CR by PE. We assume $PE \sim \text{beta}(0.4, 1.6)$. We will stop the trial if at any point that there is < 1% chance that the CR rate is > 20%. Stopping boundaries corresponding to this stopping rule and operating characteristics are listed in tables 1a and 1b. CR in the 4 months after the treatment will be included in the primary analysis.

Table 1a. Stop accrual if the number of response is equal to or less than indicated (i.e., # response) among number of patients accrued (i.e., # Patients). (PL=0.01)

# CR	0	1	2	3	4	5	6	7	8
# Pts	15	24	33	41	49	56	64	71	78

Table 1b: Operating characteristics of response (based on 10000 simulations) (PL=0.01)

True Probability	Stop Probability	Trial Sample Size Percentile		
		25%	50%	75%
0.05	0.992	15	24	33
0.1	0.735	24	41	80
0.15	0.301	64	80	80
0.2	0.086	80	80	80

b. Overall survival

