Bayesian time-to-event model will be used to monitor the overall survival [10]. Let T_e and T_s represent the overall survival time for the study and the historical treatment, respectively. We assume $T_e|Me$ and $T_s|Ms$ follow an exponential distribution with median Me and Ms , respectively. We further assume that the prior for Ms follows Inverse Gamma (IG) (35, 204) to reflect our knowledge of overall survival from the historical data, which has a mean of 6 months and a variance of 1.09. The prior for Me is assumed to be IG (3,12), which has the same mean as Ms but with a much larger variance (36) to reflect much greater uncertainty about the median time to progression of the study treatment.

The study will be monitored after the first 14 pts have been enrolled and then be repeated every month. The study will be stopped early if, based on the available data, we have little reason to believe that the median OS is 6 months or more. Formally, we'll stop the study early if there is < 5% chance that the median OS is 6 months or more. The operating characteristics of this decision rule are shown in the following table:

Table 2: Operating characteristics of Efficacy Monitoring(PL=0.05)

True Median OS (Mos)	P(Stop)	Mean Number of Pts (25%, 75%)
2	1	18 (15,20)
4	0.835	42 (21,63)
6	0.079	76 (80,80)
7	0.024	79 (80,80)

Toxicity Monitoring

Toxicity will be monitored in all pts using the method of Thall et al 1995 [9]. Toxicity is defined as non-hematologic grade 3 or 4 toxicities during the treatment course. Denote the probability of toxicity by E, where study drug related toxicity is defined as any Grade 3 or greater non-hematological toxicities. We assume $E \sim \text{beta}(0.6, 1.4)$. We will stop the trail if at any point $\Pr(E > 0.30 | \text{data}) > 0.95$, i.e. if at any time during the study, we determine that there is > 95% chance that the study drug related toxicity rate is > 30%. Toxicity monitoring will be done in cohorts and the trial will be stopped if (number of toxicity observed / among number of patients) $\geq 6/10, 8/15, 10/20, 12/25, 14/30, 16/35, 18/40, 19/45, 21/50, 23/55, 25/60, 26/65, 28/70, 30/75, \text{ and } 31/80$.

Table 3: The operating characteristics for toxicity monitoring are summarized in the following table

True toxicity probability	Probability of early stop	Sample size percentiles (10, 25, 50, 75, 90)
0.1	0	80 80 80 80 80
0.2	0.012	80 80 80 80 80
0.3	0.188	23 80 80 80 80
0.4	0.755	10 15 36 79 80
0.5	0.99	10 10 15 25 41

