Early termination of the study can be caused by either lack of efficacy or too much toxicity. If the efficacy and toxicity are considered jointly, the stopping probabilities will be higher than the probabilities shown in Tables 1 to 3.

Table 4 shows several scenarios of the joint stopping probabilities assuming that efficacy and toxicity are independent.

Table 4: Operating characteristics considering efficacy and toxicity jointly

True probability of CR	True Median OS (mos)	True Probability of Toxicity	Early Stop Probability
0.25	7	0.2	0.06
0.25	4	0.2	0.84
0.25	7	0.5	0.99
0.2	6	0.3	0.316
0.1	4	0.4	0.989
0.1	6	0.2	0.759
0.1	7	0.4	0.937

All calculations were performed using OnearmTTE and Multc99.

Trial Conduct

The Department of Biostatistics will provide and maintain a website ("Clinical Trial Conduct") for monitoring of the overall survival. The Clinical Trial Conduct website resides on a secure server, and access is gained through usernames and passwords provided to personnel responsible for enrolling patients and updating patient data. The website is accessed through a browser using secure socket layer (SSL) technology.

Personnel responsible for enrolling patients on trials will be trained in the use of the trial website, with emphasis on the importance of timely updating of follow-up times and recording of events. The monitoring rules for the overall survival will be automatically evaluated each time patient data are updated on the trial website. If the stopping rule is met, the study statistician, research nurse, and principal investigator will each receive an email notification that the stopping boundary has been met.

Analysis Plan

For discrete or categorical data, descriptive statistics will include tabulations of frequencies. For continuous data, summary statistics including n, mean, standard deviation, median, minimum and maximum will be computed. The posterior CR rate and its 95% credible intervals will be estimated. The Kaplan-Meier method will be used to estimate the probability of the overall survival.

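### Table 3 matches neither toxicity-monitoring schedule in the text: not the looks listed at 10, 15, ..., 80, and not continuous monitoring

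*Combined protocol and SAP*

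**What the plan says.** All of this is in section 10.0, Data Monitoring Plan.

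- **Criterion.** The toxicity probability E has a beta(0.6, 1.4) prior. The trial stops once the posterior probability that E exceeds 0.30 is above 0.95.
- **Timing, first statement.** The criterion applies "if at any time during the study, we determine that there is > 95% chance that the study drug related toxicity rate is > 30"%. No minimum number of patients is given.
- **Timing, second statement.** "Toxicity monitoring will be done in cohorts and the trial will be stopped if (number of toxicity observed / among number of patients") reaches 6/10, 8/15, 10/20 and so on, in steps of five patients, up to 31/80.
- **Table 3.** At true toxicity 0.1 / 0.2 / 0.3 / 0.4 / 0.5 the probability of early stopping is 0 / 0.012 / 0.188 / 0.755 / 0.99. The 10th, 25th, 50th, 75th and 90th percentiles of sample size are 23, 80, 80, 80, 80 at 0.3; 10, 15, 36, 79, 80 at 0.4; and 10, 10, 15, 25, 41 at 0.5. The table does not say which schedule was simulated.
- **Table 4** ("Operating characteristics considering efficacy and toxicity jointly") combines the toxicity figures with those for complete response (CR) and overall survival, assuming independence.

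**The concern.** Checking after every patient and checking every five patients are different safety rules with different chances of stopping. A table of operating characteristics should belong to the rule that will be run. Here the only boundaries that staff can apply are those at multiples of five, yet the printed percentiles include sample sizes at which such a trial cannot end.

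Two things are at stake. The plan does not settle whether a crossing between listed looks stops the trial. And if the listed looks are the ones used, the protection against excess toxicity is somewhat weaker than Tables 3 and 4 report.

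**Working it through.** **Inputs** (section 10.0): prior beta(0.6, 1.4), limit 0.30, cutoff 0.95, maximum 80 patients, and the listed boundaries.

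**Step 1: boundaries.** After x toxicities in n patients the posterior is beta(0.6 + x, 1.4 + n − x). The boundary at n is the smallest x with Pr(E > 0.30 | data) > 0.95. At n = 10, x = 5 gives 0.880 and x = 6 gives 0.9625, so the boundary is 6, as printed. Fourteen of the 15 printed boundaries reproduce. The exception is n = 80: x = 31 gives 0.948 and x = 32 gives 0.968, so the stated criterion gives 32/80.

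**Step 2: operating characteristics.** The number of toxicities is carried forward one patient at a time with binomial probabilities, and paths at or above the boundary are removed at each look. This is exact, with no simulation. Every outcome is taken as known at the next look. Percentiles are over all trials, including those that run to 80.

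Probability of stopping:

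| True toxicity | Table 3 | Listed looks, before patient 80 | Listed looks, counting 31/80 | Every patient from the 1st | Every patient from the 10th |
|---|---|---|---|---|---|
| 0.1 | 0 | 0.0002 | 0.0002 | 0.0016 | 0.0002 |
| 0.2 | 0.012 | 0.0107 | 0.0107 | 0.0254 | 0.0129 |
| 0.3 | 0.188 | 0.1586 | 0.1668 | 0.2150 | 0.1891 |
| 0.4 | 0.755 | 0.7031 | 0.7406 | 0.7644 | 0.7539 |
| 0.5 | 0.99 | 0.9840 | 0.9902 | 0.9907 | 0.9902 |

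If the n = 80 boundary is 32 and a crossing there counts, the listed looks give 0.161, 0.716 and 0.987 at 0.3, 0.4 and 0.5.

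Sample-size percentiles (10, 25, 50, 75, 90):

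| True toxicity | Table 3 | Listed looks | Every patient from the 1st | Every patient from the 10th |
|---|---|---|---|---|
| 0.3 | 23 80 80 80 80 | 30 80 80 80 80 | 15 80 80 80 80 | 22 80 80 80 80 |
| 0.4 | 10 15 36 79 80 | 10 15 45 80 80 | 5 12 33 76 80 | 10 15 36 79 80 |
| 0.5 | 10 10 15 25 41 | 10 10 15 30 45 | 3 7 12 23 41 | 10 10 15 25 41 |

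**Step 3: reading the comparison.**

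- *Listed looks.* A trial can end only at a multiple of 5, so 23, 36, 79 and 41 are impossible whatever is decided about n = 80.
- *Continuous wording taken literally.* The criterion is first met at 3 toxicities in 3 patients (posterior 0.976). The stopping probability is too high at 0.2 and 0.3, and the lower percentiles are too small.
- *Size against simulation error.* If Table 3 used 10,000 simulations (an assumption; that number is stated only for Table 1b), the standard error at 0.3 is about √(0.16 × 0.84 / 10,000) ≈ 0.004. The printed 0.188 is then about 8 standard errors from 0.1586, nearly 6 from 0.1668 and between 6 and 7 from 0.2150.
- *Every patient from the 10th.* All five probabilities agree within simulation error, and the percentiles at 0.4 and 0.5 match exactly. At 0.3 the cumulative stopping probability is 0.1003 at n = 22, so a simulated 10th percentile of 23 is unremarkable. A start at 9 gives 9 9 15 25 41 at 0.5, and a start at 11 gives 12 17 38 80 80 at 0.4, so of these starts only 10 fits.

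**Step 4: Table 4.** The joint stopping probability is 1 − (1 − pCR)(1 − pOS)(1 − pTox).

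- Row CR 0.2, OS 6, toxicity 0.3: 1 − 0.914 × 0.921 × 0.812 = 0.316, as printed. With 0.1586 it is 1 − 0.914 × 0.921 × 0.8414 = 0.292 (0.299 counting 31/80).
- Row CR 0.1, OS 7, toxicity 0.4: 1 − 0.265 × 0.976 × 0.245 = 0.937, as printed. With 0.7031 it is 1 − 0.265 × 0.976 × 0.2969 = 0.923 (0.933 counting 31/80).
- The other rows move by about 0.006 or less.

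**The case against.** The strongest reply is that Table 3 is not miscalculated. It is what the continuous wording gives if the first check is at the 10th patient, the smallest n in the printed list. The listed fractions could then be read as points along a continuous boundary. On that view the fault is in the wording only. The numerical gap also depends on how n = 80 is treated: counting the printed 31/80, the figure at 40% toxicity is 0.741 against 0.755. Finally, all these figures assume immediate outcomes. Toxicity is counted over the treatment course, and the plan states that "A maximum of 80 patient will be accrued at a rate of 2 to 5 patients per month", so five patients take about 1 to 2.5 months to enrol. Delay in outcomes could matter as much as the choice between the schedules.

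Part of this stands. Table 3 is a correct table for a sensible schedule, the effect is modest, and every figure here is idealised in the same way. But the start at the 10th patient is stated nowhere, patient-by-patient checking contradicts monitoring in cohorts, and no boundary is printed for the sample sizes between listed looks. Accepting the lenient reading means writing it into the plan, which is the first of the two remedies. Counting 31/80 narrows the gap in probabilities but does not remove the impossible percentiles, and a crossing once all 80 patients are enrolled cannot shorten accrual.

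**Conclusion.** The concern holds. Table 3, and the toxicity component of Table 4, describe neither schedule in the text. They agree with monitoring after every patient from the 10th; this is an inference from the numbers, not something the plan says.

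If the listed looks are used, the chance of stopping before patient 80 falls from 0.188 to 0.159 at 30% toxicity and from 0.755 to 0.703 at 40%. Counting 31/80 gives 0.167 and 0.741. Median trial size at 40% rises from 36 to 45, and the mean from 42.5 to 45.8, about 3 patients. At 20% and 50% toxicity the stopping probabilities barely change.

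The comparison rests on independent patients and immediate outcomes. The prior, the 30% limit, the 0.95 cutoff and the sample size are not in question. This should be corrected because it concerns the formal safety stopping rule, but it does not undermine the design.

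**What to change.** Choose one schedule and make the text, the boundaries and Tables 3 and 4 agree.

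**Option A: every patient from the 10th.** State this, remove the reference to cohorts, print the boundary for every n, and keep Tables 3 and 4. The stated criterion gives: 6 at n = 10; 7 at 11–12; 8 at 13–15; 9 at 16–18; 10 at 19–20; 11 at 21–23; 12 at 24–25; 13 at 26–28; 14 at 29–31; 15 at 32–34; 16 at 35–36; 17 at 37–39; 18 at 40–42; 19 at 43–45; 20 at 46–48; 21 at 49–50; 22 at 51–53; 23 at 54–56; 24 at 57–59; 25 at 60–62; 26 at 63–65; 27 at 66–68; 28 at 69–71; 29 at 72–73; 30 at 74–76; 31 at 77–79; 32 at 80. The cost is wording and a longer list, plus toxicity data that are current at each enrolment. No new simulation is needed.

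**Option B: looks every five patients.** Delete the continuous wording, say whether a crossing at n = 80 counts as an early stop, and recompute Table 3 and the toxicity part of Table 4. If n = 80 does not count, the stopping probabilities are 0.000 / 0.011 / 0.159 / 0.703 / 0.984, with the listed-look percentiles shown in the working. The cost is rerunning one table and part of another, and the reported figures become slightly less favourable.

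Neither option adds patients.

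Two small corrections can be made at the same time. Reconcile 31/80 with the criterion, which gives 32/80; this has almost no practical effect once accrual is complete. Also state the starting point of the CR rule. It says "We will stop the trial if at any point that there is < 1% chance that the CR rate is > 20"%, which is first met at 0 responses in 13 patients (posterior 0.0080), whereas Tables 1a and 1b are consistent with a start at 15.

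### The last listed toxicity boundary, 31/80, falls just short of the plan's own 95% rule (0.948); the rule gives 32/80

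*Combined protocol and SAP*

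**What the plan says.** Section 10.0, Toxicity Monitoring, sets out a Bayesian stopping rule for grade 3 or higher non-hematologic toxicity. The prior for the toxicity probability E is beta(0.6, 1.4). The rule is written once as a formula, Pr(E > 0.30 | data) > 0.95, and once in words: the trial stops if "there is > 95% chance that the study drug related toxicity rate is > 30" per cent.

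The same paragraph then turns the rule into counts: "Toxicity monitoring will be done in cohorts and the trial will be stopped if" the number of toxicities reaches a listed value at 10, 15, 20 and so on up to 80 patients. The list runs from 6/10 and ends "28/70, 30/75, \text{ and } 31/80". The section also fixes the sample size: "A maximum of 80 patient will be accrued". The last listed look is therefore at full enrolment.

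Table 3 gives early-stop probabilities of 0, 0.012, 0.188, 0.755 and 0.99 at true toxicity rates of 0.1 to 0.5. Table 4 gives joint stopping probabilities for efficacy and toxicity.

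**The concern.** The list is meant to be the posterior rule expressed as counts, so each entry should be the smallest count at that sample size whose posterior probability exceeds 0.95. The last entry is not. At exactly 31 toxicities in 80 patients, the list says the boundary is reached and the rule says the threshold is missed. The plan does not say which of the two governs.

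A pre-specified safety rule should give one answer for one set of data. Accrual would be complete at that look, but patients could still be on treatment (up to 12 consolidation cycles are allowed in Section 5.1), and safety is a secondary objective.

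**Working it through.** **Inputs, all from Section 10.0.** Prior beta(0.6, 1.4); limit 0.30; cutoff strictly above 0.95; the 15 listed boundaries; maximum of 80 patients.

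**Formula.** With x toxicities in n patients, E | data ~ Beta(0.6 + x, 1.4 + n − x). The boundary at n is the smallest x for which Pr(E > 0.30 | data) > 0.95.

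**Reproducing the list.** For each entry, the posterior probability at one count below the listed value and at the listed value:

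| n | Listed x | Pr at x − 1 | Pr at x |
|---|---|---|---|
| 10 | 6 | 0.880 | 0.963 |
| 15 | 8 | 0.893 | 0.960 |
| 20 | 10 | 0.906 | 0.961 |
| 25 | 12 | 0.918 | 0.963 |
| 30 | 14 | 0.929 | 0.967 |
| 35 | 16 | 0.938 | 0.970 |
| 40 | 18 | 0.946 | 0.973 |
| 45 | 19 | 0.914 | 0.953 |
| 50 | 21 | 0.926 | 0.959 |
| 55 | 23 | 0.936 | 0.964 |
| 60 | 25 | 0.945 | 0.969 |
| 65 | 26 | 0.921 | 0.952 |
| 70 | 28 | 0.931 | 0.958 |
| 75 | 30 | 0.940 | 0.964 |
| 80 | 31 | 0.918 | **0.948** |

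The first 14 entries are exactly the smallest counts that cross 0.95, which confirms the prior, limit and cutoff. The last does not cross:

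- 31/80: Beta(31.6, 50.4), Pr(E > 0.30) = 0.9480, not above 0.95.
- 32/80: Beta(32.6, 49.4), Pr(E > 0.30) = 0.9684, above 0.95.

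Applied patient by patient, the rule gives 31 at n = 77, 78 and 79 (0.969, 0.963, 0.956) and moves to 32 at n = 80. The 31 may have been carried forward from those sample sizes, but the plan does not say so.

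**Size of the effect.** The exact stop probability over the 15 listed looks comes from carrying the distribution of the toxicity count forward five patients at a time (ten at the first look) and removing the paths that reach a boundary:

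| True rate | With 31/80 | With 32/80 | Difference |
|---|---|---|---|
| 0.30 | 0.167 | 0.161 | 0.006 |
| 0.35 | 0.429 | 0.410 | 0.019 |
| 0.40 | 0.741 | 0.716 | 0.024 |

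The differences are taken before rounding. Each is the probability of reaching 80 patients with exactly 31 toxicities: 0.6%, 1.9% and 2.4%.

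**Whether Tables 3 and 4 used the entry.** Stop probabilities at true rates 0.2, 0.3, 0.4 and 0.5:

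- Table 3 as printed: 0.012, 0.188, 0.755, 0.99.
- Posterior rule after every patient from n = 10: 0.013, 0.189, 0.754, 0.990. These do not change if the n = 80 look is dropped. A trial still open after patient 79 has at most 30 toxicities, so at most 31 at n = 80, which is below 32.
- Listed looks with 31/80: 0.011, 0.167, 0.741, 0.990.
- Listed looks with 32/80: 0.011, 0.161, 0.716, 0.987.

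Table 3 fits the every-patient schedule. Its sample-size percentiles include 23, 36 and 79, which looks at multiples of five could not produce. Table 4 carries Table 3 forward by independence: for CR 0.2, median OS 6 months and toxicity 0.3, 1 − (1 − 0.086)(1 − 0.079)(1 − 0.188) = 0.316, as printed.

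**The case against.** The best defence is that this hardly matters. The miss is 0.2 percentage points and the error is cautious. It shows only at exactly 31/80, when no further patient can be enrolled. The rule also speaks of stopping at any point. Read that way, a 31st toxicity by patient 77, 78 or 79 stops the trial anyway, and the conflict arises only if patient 80 supplies the 31st: 0.25% at a true rate of 0.30 and 1.0% at 0.40. The posterior rule stands directly before the list, so a statistician could settle the case from it. All of this stands, and it is why the point is minor.

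It does not make the entry right. Rounding does not rescue it: if 0.948 counted as 0.95, then 17/40, at 0.946, would count too, and the plan lists 18/40. Other priors, an uncertain historical rate with mean 0.30, and an exact binomial tail were also tried, and none reproduces the whole list. A cutoff between about 0.946 and 0.948 would, but the plan states 0.95 both in the formula and in words.

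Three stronger readings are tempting, and the documents do not support them:

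- *The list condemns a regimen that the rule clears.* A posterior probability of 94.8% narrowly misses a threshold; it is not evidence that the toxicity rate is acceptable.
- *The look at 80 decides whether the completed trial is declared too toxic.* The plan speaks only of stopping, and its Analysis Plan contains no final toxicity declaration.
- *Tables 3 and 4 are wrong because of this entry.* Table 3 follows a schedule in which the n = 80 look has no effect, and Table 4 inherits its figures. The gap between that schedule and the listed cohorts is a separate matter, and it exists with either value at n = 80.

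**Conclusion.** The entry is wrong as written, and the point is minor. Under the stated prior, limit and cutoff, the boundary at 80 patients is 32, not 31. That conclusion needs only the figures in Section 10.0 and the beta-binomial update.

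The error adds between 0.6 and 2.4 percentage points to the probability of a toxicity stop for true rates of 0.30 to 0.40, always in the direction of stopping, and changes no enrolment. Those figures further assume independent patients with a common toxicity rate, looks only at the listed sample sizes, complete toxicity data at each look, and no stopping for response or survival.

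**What to change.** In Section 10.0, Toxicity Monitoring, change the last boundary from 31/80 to 32/80, the value the stated 0.95 cutoff gives. A short sentence saying that the posterior rule governs if it and the list ever differ would remove any remaining doubt.

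The cost is one number, and the final look becomes slightly less strict, as the rule requires. Tables 3 and 4 need no recomputation on account of this change.

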7.0 Evaluation During Study

CBC with differential and platelet counts at least weekly while on therapy and every 4 to 8 weeks thereafter as long as on study. No differential is needed if the WBC is $< 1.0 \times 10^9/L$.

Chemistry profile (at least creatinine, SGOT or SGPT, total bilirubin, potassium, magnesium) every two weeks while on therapy, then every 4 to 8 weeks as long as on study.

Bone marrow aspirate and/or biopsy at the end of course 1 (day 28 +/- 7 days). If a patient is not in remission at this point, further bone marrow aspirate and/or biopsy can be scheduled as per the investigator's discretion and mandated by the development of the peripheral blood counts.

No repeat bone marrow is necessary if non-response or progressive disease can be unequivocally diagnosed from peripheral blood tests, or, in patients with a WBC \leq 0.3 if the bone marrow test is considered non-contributory by the investigator at any time point.

Follow up marrow tests should include cytogenetic analysis for those patients who had abnormalities prior to therapy start.

Repeat physical examination (problem focused) prior to administration of each course

After completion of therapy and as long as still on study, patients will return to MD Anderson Cancer Center for repeat physical examination (problem focused), repeat CBC with differential and platelet count, and chemistry profile (at least creatinine, SGOT or SGPT, total bilirubin, potassium, magnesium) every 6 months (+/- 2 months). A CBC with differential and platelet count should be checked every one to two months, but these blood tests may be done locally.

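### The overall-survival stopping rule is planned for monthly looks but run at every data update, with no common cut-off date, so the stopping probabilities in Table 2 are not assured

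*Combined protocol and SAP*

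**What the plan says.** Section 10.0, under b. Overall survival, gives a calendar schedule: "The study will be monitored after the first 14 pts have been enrolled and then be repeated every month". The decision rule is: "we'll stop the study early if there is < 5% chance that the median OS is 6 months or more". The model is exponential, with inverse-gamma priors for the medians Me (study) and Ms (historical). Table 2 reports stopping probabilities of 1, 0.835, 0.079 and 0.024 at true medians of 2, 4, 6 and 7 months.

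Trial Conduct, in the same section, gives a different trigger: "The monitoring rules for the overall survival will be automatically evaluated each time patient data are updated on the trial website". When the rule is met, the statistician, the research nurse and the principal investigator are e-mailed. Staff are trained to keep follow-up times and events up to date, but no update interval or data cut-off is given.

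Section 7.0 asks for blood counts at least weekly on therapy. After therapy, while the patient remains on study, return visits to the centre are "every 6 months (+/- 2 months). A CBC with differential and platelet count should be checked every one to two months"; the blood counts may be done locally.

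**The concern.** There are two separate issues.

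**Number of looks.** Table 2 is presented with a monthly schedule. A rule run at every update looks more often and has more chances to cross by accident.

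**Data at each look.** Under an exponential model the posterior depends on the data only through the number of deaths and the total follow-up time. When a death is entered, the rule runs with that death counted, while each living patient contributes time only to the last update of that patient's record. If deaths reach the database faster than confirmations of survival, follow-up time is short relative to deaths and the posterior median is too low. This can happen at monthly looks too, so settling the look schedule does not cure it.

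OS is a co-primary endpoint and this rule can end accrual. At stake is whether a regimen that meets its 6-month target is stopped about as rarely as Table 2 says.

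**Working it through.** **Inputs from Section 10.0.** Me has prior IG(3, 12) and Ms has prior IG(35, 204); survival is exponential; the cutoff is 0.05; 80 patients at 2 to 5 per month; first look at 14 enrolled, then monthly.

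**Prior check.** For IG(a, b), mean = b/(a−1) and variance = b²/[(a−1)²(a−2)].
- Ms: 204/34 = 6; 204²/(34² × 33) = 36/33 = 1.09.
- Me: 12/2 = 6; 144/(4 × 1) = 36.

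All four agree with the plan.

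**Posterior.** With d deaths and total follow-up T months, Me | data ~ IG(3 + d, 12 + ln2 × T). Stop if Pr(Me > Ms | data) < 0.05.

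**Which comparator.** Comparing Me with the random historical Ms approximately reproduces Table 2. Comparing Me with a fixed 6 months, the literal reading of "there is < 5% chance that the median OS is 6 months or more", gives about 0.245 at the target and 0.983 at 4 months, against the stated 0.079 and 0.835. That mismatch is a separate issue, so only the Me-versus-Ms rule is used below.

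**Reproducing Table 2.** Monthly looks from the 14th to the 80th enrolment, follow-up fully current, 2 patients per month, 20,000 simulated trials:

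| True median (months) | Table 2 | Simulated |
|---|---|---|
| 2 | 1 | 1.000 |
| 4 | 0.835 | 0.836 |
| 6 | 0.079 | 0.089 |
| 7 | 0.024 | 0.030 |

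Agreement is within about one percentage point. At 3 and 5 patients per month the 6-month figure is 0.08 to 0.09.

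**How stale follow-up moves the boundary.** With 10 deaths the rule stops when recorded T is 43.8 months or less. Suppose true T is 50 months and 10 living patients' records are each 1 month behind. Recorded T is 50 − 10 × 1 = 40, and the boundary is crossed although the current data would not cross it.

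**Stopping probability at a true median of 6 months.** The lag is an assumption: the documents give no update interval.

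| Scenario | P(stop) |
|---|---|
| Monthly looks, all data current | about 0.09 |
| Look at every death, all data current | about 0.11–0.13 |
| Monthly looks, deaths current, only patients beyond 4 months lag by up to 2 months | about 0.12–0.13 |
| Monthly looks, deaths current, all survivors lag by up to 1–2 months | about 0.14–0.30 |
| Monthly looks, deaths and survival status equally delayed | about 0.08–0.10 |

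In the fourth row, at 3.5 patients per month, the figures are 0.16 for a lag of up to 1 month and 0.24 for up to 2 months. Partial asymmetry falls in between: at the same accrual rate, a survivor lag of up to 2 months with a death delay of up to 1 month gives 0.15.

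**Both features together.** With a look at every death, deaths current, and all living patients updated only every 1 to 2 months, the figures are 0.16 to 0.21 at 2 patients per month and 0.26 to 0.42 at 5 per month. This stacks the one-sided lag on the more frequent looks and marks the unfavourable end.

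**The case against.** A reader might infer that update-triggered evaluation by itself pairs current deaths with stale survivors, that the error always runs toward false futility, and that an on-target regimen would therefore be stopped far too often. The documents do not support this.

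- **The lag is not stated.** Training stresses timely entry of follow-up times and of events alike. Deaths are captured as serious adverse events only until 30 days after the last dose. Beyond that, the documents give no faster route for learning of a death than for confirming survival.
- **The direction is conditional.** With equal delays the inflation disappears.
- **The long contact intervals are post-therapy.** On therapy, counts are at least weekly, and therapy may run to 3 + 12 = 15 cycles. A survivor lag of up to one week gives 0.10 to 0.11.
- **Crossing sends an e-mail.** No automatic closure is described, so the data can be checked first.

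These points stand, and they limit the size and certainty of the problem. They do not remove it. The two schedules still conflict. The e-mail is described as notice that the boundary has been met, with no step to refresh the data written down. An asymmetry remains plausible: deaths within the safety window must be reported to the IRB within set timeframes, while confirming survival has no deadline. Patients who leave the study for progression, or for lack of improvement after three induction cycles, have no stated survival contact schedule at all.

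**Conclusion.** The concern holds in a limited form. The monthly schedule stated with Table 2 and the update-triggered evaluation under Trial Conduct are not the same rule, and neither comes with a common cut-off.

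With current data the cost is small: about 0.11 to 0.13 against 0.09 simulated for monthly looks (0.079 stated). A larger effect needs deaths to be entered sooner than survivor follow-up. It is then about 0.12 to 0.13 if only longer-term patients lag, and about 0.14 to 0.30 at monthly looks if all survivors lag by up to 1 to 2 months. These figures assume exponential survival, the Me-versus-Ms comparison and accrual within the planned range.

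This is a cheap improvement to a rule on a primary endpoint, not a flaw that must be cured before the trial can be trusted. Figures from the fixed 6-month reading should not be used to enlarge it.

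**What to change.** Reconcile the two parts of Section 10.0 with one paragraph:

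- Apply the OS rule once a month from the 14th patient, at a single stated cut-off date.
- Before each look, confirm every living patient's status to that date, including patients who have left the study. Censor all follow-up there and ignore later deaths.
- If some patients cannot be confirmed, move the cut-off back to the last date to which all are known.
- Treat website e-mails between looks as alerts to refresh the data, not as the stopping boundary.

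The cost is a monthly status update and a rule that runs a few weeks behind real time. In simulation, even a common cut-off set 2 months back returned the stopping probability at the 6-month target to 0.09.
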